Prospective associations between screen media use and physical activity in preschool children: Findings from the Motor Skills in PreSchool (MIPS) study

- *Statistical analysis plan*

Last edited

28-04-2020

Background

Time spent using screen-based media devices is ubiquitous in everyday life of children and adults of the 21st century. Rapid technological development and market introduction of handheld screen-based devices, such as smartphones and tablets, to consumers all over the world, has changed the way and the amount of time humans interact with electronic media. To the extent that self-report depicts screen time habits accurately, evidence suggests that British children and youth (8-18 years) engage in four hours and 45 minutes of screen time a day on average, as a main activity or while engaging in other activities (1). Furthermore, results from the same study indicate a pronounced increase in screen time from 2010 to 2015 in British children (1) and data from North America suggests an increase in computer use during leisure hours from 2001 to 2016 in most age groups (2). Based on a 2018 survey of 3660 school children in Denmark, 24% of boys and at least 19% of girls aged 13 and 15 spend at least four hours each weekday watching movies, tv-series, Youtube-movies or entertainment shows (3). Also, 88% of adult Danes report using the internet as part of their daily routine (4). Clearly, adults and children spend much of their leisure time engaging in some form of entertainment-based screen media.

In the mainstream media and in the general population, there is much discussion about whether use of screen media carries a risk to our mental well-being and physical health. According to a 2016 Technical report from The American Academy Pediatrics, screen-based media use includes some beneficial effects, such as improved knowledge acquisition at an early age, access to important information and creating enhanced opportunities for communication (5). However, there is also evidence which suggest that screen media use has a negative relationship with children and adolescents' sleep (6), as well as multiple other aspects of health, including adiposity, unhealthy dietary pattern, symptoms of depression, a poor quality of life (7) and decreased physical activity (8). Of concern may be the effect of excessive screen time in childhood on children's physical activity habits.

Physical activity in children below five years has been associated with numerous health benefits, including improved motor skills and cognitive development, cardiometabolic health, decreased adiposity (9), and possibly increased psychosocial health (10). Also, some evidence suggests that childhood physical activity habits track to some degree into young adulthood (11) which furthermore underlines the importance of physical activity at an early age. Therefore, preschool years appear to be an important time to establish healthy physical activity habits to support a healthy physical, psychological, and social development throughout childhood. Thus, it is very important to understand the physical activity behavior of young children, as well as map which factors it is associated with.

The relation between screen time usage and device-based assessment of physical activity in pre-school children is still poorly understood. Most cross-sectional analyses investigating this relation have found no association (12-16), while two found inverse associations (17, 18) and one found a counter-intuitive positive association (in girls only) (16). Of these, six are studies of correlates (12-14, 16, 17, 19). Statistical model building in these investigations is not necessarily based on variable selection in order to analyze the relation between screen time and physical activity with appropriate adjustment for confounding. For this reason, over-, under- or inappropriate statistical correction may at least partly explain somewhat conflicting findings. No prospective analyses of observational data using objective measures of physical activity have been published in this age group. Results from two randomized controlled trials, whose interventions aimed to decrease screen time in preschool children, have been published (20, 21). In Epstein et. al. 2008 (20), a tv-reduction intervention did result in significant change in device-based assessment of physical activity, in 4-7 year old children. In the pilot randomized controlled trial by Hinkley et. al. 2015, including 2-3-year-old children, a screen media use reduction intervention did not result in change in accelerometry-derived physical activity, either (21). Overall, there are clear gaps in our knowledge of the relation between screen media use and physical activity in preschool children,

Time spent in distinct activity types (sitting, moving, standing, biking, running, walking, and lying down) are determined from the acceleration measured with the thigh worn device using the method proposed by Skotte et. al. (2014) (23) using 1-second epochs. In this study, the method was validated with adults in a standardized field test and demonstrated a sensitivity >95% and specificity >99% for all activities. Also, during almost six days of measurement in free-living, sensitivity and specificity were 98% and 93%, respectively, for classification of sitting time (23). Child specific decision thresholds for the method were developed using an internally conducted study (publication in preparation). The results indicate high sensitivity and specificity of measurement. Non-sedentary time is defined based on this method and includes all activities, including standing, other than sitting and lying. We will analyze non-sedentary time as the amount per day (total amount per six days divided by six). In addition, time spent within physical activity intensity domains (sedentary, light, moderate and vigorous) will be estimated using ActiGraph counts generated with the waist worn device (24) using 10-second epochs. The cut-points defining intensity domains are determined using pre-school specific accelerometer cut-points (25).

Based on the child's daily schedule data during physical activity assessment, we will separate physical activity performed according to time of sleep (including naptime in preschool), leisure, and preschool hours. If data schedule is missing, we will impute using data from preceding or following days, where data is available. If no data on nocturnal sleep time is not available from daily schedules, typical sleep hours reported in the baseline questionnaire, will be employed. Because schedules are completed at both baseline and follow-up physical activity assessment, we will be able to employ time-specific data on sleep time. This is necessary, as sleep patterns most likely have changed from baseline to follow-up, i.e. 18 months later, when the children are that much older.

Statistical analyses

To address the primary objective, we will analyze changes in screen time (based on weighted averages of typical weekday and a typical weekend day) as continuous variable, as well as using four categories of screen time; those who consistently, i.e. at both baseline and 18-month follow-up, have high screen time; those who initially had high screen time but moved to having low screen

time at 18-month follow-up; those who initially had low screen time but moved to the high screen time category; and, lastly, those consistently had low screen time. High screen time will be defined as being above the 1-hour recommendation by WHO for daily sedentary screen time (9). However, the median baseline screen time will be used as a cut-off, if an inspection of the data distribution deems this more appropriate. The secondary objective of the study proposal will be addressed using the same treatment of the exposure variable, as in the primary objective.

To address possible clustering of preschool children's non-sedentary time within their respective preschools a multilevel modelling approach will be used to assess the relation of screen time with physical activity. We will employ a linear mixed-effect model, where the random effect (random intercept) of preschool will be included. A crude model (only adjusting for age, sex, and intervention arm) and a multivariable adjusted model will be computed. Although the main effect of intervention will be computed in our statistical model, this will not be presented in the paper. This remains to be true even in the unlikely event that an editor or reviewer request this information from us.

According to a proposed Directed Acyclic Graph of the relation between screen time and physical activity (appendix 1), to analyze the direct relation (close all backdoor confounding paths) we could adjust for the child's age, both the child's and the parents' chronic disease status, gender, the child's mental well-being, number of siblings, whether the child has access to his or her own garden, as well as parents' screen media use habits and the household socio-economic-status. Of several minimally adjustment sets, this set of variables is chosen as questions pertaining to these variables were posed in the questionnaires included in MIPS. We will also adjust for baseline non-sedentary time to into account that one's initial levels may be related to the degree of change in screen time and independently predict changes in non-sedentary, over time. If some variables exhibit large amounts of missing data, these may not be included in the main model. Rather, they will be included in a sensitivity analysis and missing data will be imputed (see later). If variables exhibit lack of variation, they may be excluded from the main analysis, and, instead, including in a sensitivity analysis.

First, it is well-established that males and females have different health behaviors. Thus, it is important to investigate potential sex differences between changes in screen time and changes in non-sedentary time during leisure. Secondly, socio-economic-status may to some extent reflect parent resources. Resources may to some extent dictate whether parents have the capacity to consistently encourage their children to perform more daily physical activity, even though their children have plentiful screen time. Thus, the extent to which parents can mitigate the risk of physical inactivity with increasing screen time, may differ depending on available physical and mental resources. It is, for this reason, important to investigate whether the relationship between changes in screen time and changes in non-sedentary differ depending on the socio-economic group which the parents report membership. Lastly, related to the above, the number of immediate siblings may also encourage physical activity, through e.g. an invitation to play activities. Such encouragement may be absent in only children. Overall, effect modification of gender, socio-economic status proxy (parent education) and number of siblings (single-child/having siblings only two years younger or older than oneself/having siblings more than two years younger or older than oneself) will be tested using the likelihood ratio test (comparing a model with and a model without the respective interaction term). We will conduct these analyses only in the analyses included in the primary aim.

Supplementary analysis of the primary analysis

- The analyses included in the primary aim will be parsed (via stratification) onto weekdays and weekend days. The purpose of this is to investigate whether the strength of the relationship between changes in screen time and changes in non-sedentary time during leisure differ, depending on the day of week (typical weekday or typical weekend day).

Sensitivity analyses of the primary analysis

- In the MIPS study, the accelerometers were mounted to the children's skin using adhesive tape at baseline and using belts at 18-month follow-up. Cross-sectional analysis of the relation between screen time at baseline and follow-up, with non-sedentary time at baseline and follow-up, respectively. The purpose of this is to investigate whether we have reasons to suspect that methodological issues relating to the modality of accelerometry, might impact the computation of amount of participation in daily activities and time spent at distinct activity types. These investigations will be conducted in children who are five at baseline and who are five at 18-month follow-up (two separate cohorts), i.e. in subsets of the data. We will also compare the amount of wear time at the two time points.
- We will also conduct an analysis where we limit the exposure variable to baseline screen time (i.e. not changes in screen time) and relate this to changes in non-sedentary time during leisure. In the analyses included in the primary aim, concerns regarding reverse causality may be raised, which we will attempt to address in this analysis. This approach assumes that to some extent screen time habits are relatively constant in the 18 months that follow.

- To address the possibility of bias from missing data, e.g. from loss to follow-up (not participating in follow-up examination) or other reasons, we will compute, based on the models from the primary aim, where we impute data on covariates and exposure variable using Multiple Imputation Chained Equations. A mixed-effect model including beta-coefficient and 95% confidence intervals will be computed based on 20 datasets. Our a priori assumption is that missing data is missing at random (MAR).

We will check all the linear mixed effect models for the basic statistical assumptions, which underlie the integrity of the models. We will visually assess normality of residuals, linearity of each independent variable to the dependent variable, homogeneity of variance of the residuals, as well as check that means from the fixed effect of the cluster groups are not correlated with the effects associated with the cluster variable groups.

The statistical analyses will be conducted using Stata IC 16 (Statacorp) with an $\alpha=0.05$ (two-sided testing).

Data storage

The data will be stored it on a PF-folder, on a University server. A PF folder is a type of folder which meets the requirements of the General Data Protection Regulation (including logging of user folder activity) for storage of sensitive data. The data will be deleted when the study has been finalized in accordance with the legal agreement established with SDU Research and Innovation.

Variables proposed

Variable	Variable names	Baseline (Autumn 2016)	Follow-up (Spring 2018)
Child variables			
All variables on the child's screen media use habits	screen_morning_bl screen_evening_bl screen_workhour_bl screen_workmin_bl screen_weekhour_bl screen_weekmin_bl tv_workhour_bl tv_workmin_bl tv_weekhour_bl tv_weekmin_bl screenrules_bl (only baseline) screenrule_control_bl (only baseline)	x	x
Child's age/date of birth	birthdate	x	
Child's gender	gender	x	
Child's height	height_ant	x	
Child's weight	weight_ant	x	
Child country of birth	childnative_bl childnativeother_bl	x	
Number of siblings	cohabchildren_bl	x	
Age of siblings	sib1birthDatofelt_bl sib2birthDatofelt_bl sib3birthDatofelt_bl sib4birthDatofelt_bl sib5birthDatofelt_bl sib6birthDatofelt_bl	x	
Wake and sleep times of the child (baseline survey data)	wakeworkday_bl wakeworkdaywhen1_bl wakeworkdaywhen2_bl sleepworkday_bl sleepworkdaywhen1_bl	x	

	sleepworkdaywhen2_bl wakeweekend_bl wakeweekendwhen1_bl wakeweekendwhen2_bl sleepweekend_bl sleepweekendwhen1_bl sleepweekendwhen2_bl		
Wake, sleep and nap time according to daily schedule registrations	Provided by [name]	x	x
Child's chronic disease state	genhealth_bl inhealth_bl inhealthtype_bl psydiag_bl psydiagtx_bl	x	
Type of home and whether the child has access to his/her own garden	houseown_bl housetype_bl housetypeother_bl garden_bl		
Child's mental wellbeing (Strengths and difficulties questionnaire – total score)	complete_triv_paed16au complete_triv_paed18sp	x	x
Immediate family (including father and mother) musculoskeletal disease	famill_bl famill_pain_bl famill_rharth_bl famill_osarth_bl famill_other_bl famill_none_bl famill_othertx_bl	x	
Kindergarten	key_kindergarten	x	
Intervention/randomization arm	?	x	
Accelerometry-derived physical activity data	Provided by [name]	x	x
Parent/caregiver variables			
Biological mother's country of birth	motnative_bl	x	
Biological father's country of birth	fatnative_bl	x	
Mother's education	motedu_bl		
Father's education	fatedu_bl		
All variables on the mother's screen media use habits	screenmot_workhour_bl screenmot_workmin_bl screenmot_weekhour_bl screenmot_weekmin_bl	x	
All variables on the father's screen media use	screenfat_workhour_bl screenfat_workmin_bl screenfat_weekhour_bl screenfat_weekmin_bl	x	

Publication plan

A manuscript will be written based on the results of the current study and submitted to a peer-review journal. The journal that the journal will be submitted to is not decided at this point. The results of the current investigation will be submitted independently of

the direction of the findings, including non-significant results. All authors list above will be included as authors of the manuscript, unless an author chooses not to take part in the study.

Appendix 1 – Suggested Directed Acyclic Graph of causal relation between screen media use and non-sedentary time in preschool children (SES: Socio-economic-status, P: Parental, ST: Screen time, PA: Physical activity)

Reference list

1. Mullan K. Technology and Children's Screen-Based Activities in the UK: The Story of the Millennium So Far. *Child Indicators Research*. 2018;11(6):1781-800.
3. Statens Institut for Folkesundhed. Skolebørnsundersøgelsen 2018 - Helbred, trivsel og sundhedsadfærd blandt 11-, 13- og 15-årige skoleelever i Danmark. 2019.
4. Danmarks Statistik. It-anvendelse i befolkningen 2018. 2018.
9. WHO. Guidelines on physical activity, sedentary behaviour and sleep for children under 5 years of age 2019.

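### The weekday/weekend analysis is meant to show whether the association differs by day type, but the SAP plans only separate stratum fits and no estimate, interval or test of the difference

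*SAP*

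**What the plan says.** The section Supplementary analysis of the primary analysis contains one item. Its method is that the primary-aim analyses "will be parsed (via stratification) onto weekdays and weekend days". Its aim is comparative: "The purpose of this is to investigate whether the strength of the relationship between changes in screen time and changes in non-sedentary time" in leisure differs, "depending on the day of week (typical weekday or typical weekend day".

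The paragraph just before it, at the end of Statistical analyses, treats three other modifiers (gender, parent education and number of siblings) formally. Each "will be tested using the likelihood ratio test (comparing a model with and a model without the respective interaction term". Day type is not on that list.

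The model for the primary aim, also under Statistical analyses, is a linear mixed model "where the random effect (random intercept) of preschool will be included". No other random effect is named. The exposure is the change in a weighted average of weekday and weekend-day screen time.

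**The concern.** A question of the form 'does the association differ between A and B?' is answered by an estimate of the difference with its uncertainty. Two slopes, each with its own interval, do not give that. The SAP accepts this for gender, parent education and siblings, where it plans a formal comparison. It then asks the same kind of question about day type and plans only the split.

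Day type also differs from those modifiers because it varies within a child. Largely the same children appear in both strata, so the two slopes are not independent estimates. A reader given only the stratum results does not know their covariance and so cannot give an interval for the difference its correct width. At stake is whether this supplementary analysis answers its own question. The primary result is not at stake.

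**Working it through.** The SAP states no figure for this analysis, so there is nothing to reproduce. The check has two parts.

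**1. Is a contrast planned anywhere?**
- Supplementary analysis: stratification only.
- Statistical analyses: interaction tests for three named modifiers, none of them day type.
- Sensitivity analyses: coefficients with 95% confidence intervals are mentioned for the multiple-imputation model, and a general two-sided alpha of 0.05 is set. Neither is a weekday/weekend contrast.

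So no difference, interval or test is planned.

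**2. What does the missing covariance do?**

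The primary exposure combines both day types, and the table under Variables proposed lists two sets of daily screen-time fields per child (work and week). A child in the primary analysis therefore has a screen-time value for each day type.

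Let the more precise stratum slope have standard error s, the other k·s, and let r be the correlation between the two slope estimates.
- Correct SE of the difference: s·√(1 + k² − 2rk).
- SE from the two separate fits with the covariance left out: s·√(1 + k²).
- Ratio of the second to the first: √[(1 + k²)/(1 + k² − 2rk)].

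All inputs are assumptions: k from 1 to 2, and r = 0 or 0.3. For simple slopes fitted on the same children, r is roughly the correlation of the two exposures times the correlation of the two residuals. Assumed values of 0.6 and 0.5 give 0.6 × 0.5 = 0.30.

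| k | SE without covariance (also correct at r = 0) | Correct SE at r = 0.3 | Ratio at r = 0.3 |
|---|---|---|---|
| 1 | √2 = 1.41 s | √1.40 = 1.18 s | 1.20 |
| 1.5 | √3.25 = 1.80 s | √2.35 = 1.53 s | 1.18 |
| 2 | √5 = 2.24 s | √3.80 = 1.95 s | 1.15 |

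At r = 0.3 the interval without the covariance is 15-20% too wide. At r = 0 it is correct. The third column also shows that a properly computed contrast is less precise than the better stratum slope: its standard error is 1.18 to 1.95 times as large at r = 0.3.

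**The case against.** The best defence is that the split is deliberately descriptive. It is labelled supplementary, its aim is only to investigate, and the paragraph before it reserves formal testing for three named modifiers. That supports a low severity. It does not remove the mismatch, because the stated purpose is still to learn whether the strength of association differs.

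A reader might infer three stronger things, none of which the SAP supports.
- **That no valid interval could be formed from the published strata.** With zero or positive correlation between the slopes, combining the two separate standard errors gives an interval that is correct or too wide. It is inefficient, not invalid. It would be too narrow only under negative correlation, and nothing in the SAP suggests that. A much larger excess than 15-20% needs a higher correlation, for which the SAP gives no basis either.
- **That the plan carries a high false-positive rate.** If the true slopes were equal, power were 50% in each stratum and the estimates were independent, exactly one stratum would be significant with probability 2 × 0.5 × 0.5 = 50%. But the SAP does not say that differences will be judged by comparing significance, so no error rate can be attributed to it.
- **That the preschool-only random effect is a fault of the primary model.** That model appears to have one change value per child, so a child-level effect would have no role in it. Within-child dependence matters only once the two day types are analysed together.

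**Conclusion.** The point stands as a minor one. The stated purpose is comparative, the only planned method is separate fits, and no section supplies the difference. Followed as written, the plan describes each day type without answering its own question. Each stratum estimate is sound as a description, and the primary estimate is unaffected.

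That the contrast is missing rests on the text alone. The 15-20% rests wholly on assumed inputs (slope correlation 0.3, ratio of standard errors 1 to 2), because the SAP gives no sample size, number of preschools, standard deviation or correlation. It illustrates why the covariance matters and is not an estimate for this study.

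**What to change.** Keep the stratum estimates and add one pre-specified contrast: the weekday-minus-weekend difference in slopes, with a 95% confidence interval, for the multivariable-adjusted model with continuous exposure.

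- **Data.** State that screen-time change, the non-sedentary-time outcome and the baseline non-sedentary-time adjustment are all specific to day type. The current text does not settle this explicitly.
- **Model.** Stack the two day types and include a day-type-by-exposure interaction. Allow for the same child appearing twice and for clustering by preschool. Two examples are a within-child covariance plus the preschool effect, or preschool-level clustering with a small-sample reference distribution. Name the method chosen.
- **What to avoid.** Copying the likelihood ratio interaction test onto stacked data with only the preschool intercept would ignore the within-child correlation.

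The cost is one additional model on data already collected, plus a few lines of SAP text. The downside is low precision, so a wide interval should be reported as inconclusive and not as evidence of no difference.

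If the contrast is not wanted, label the strata descriptive, reword the purpose sentence and draw no conclusion about a weekday/weekend difference. That costs a sentence or two of SAP text.
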